# 1 BACKGROUND

## 1.1 BACKGROUND AND RATIONALE

This is an open-label study, to evaluate the anti-tumoral activity of erlotinib (Tarceva®) through objective response rate (ORR) in patients with non-small-cell lung cancer (NSCLC) in locally advanced or metastatic stages who have not received previous chemotherapy for their disease and who present activating mutations in the tyrosine kinase (TK) domain of the epidermal growth factor receptor (EGFR).

### 1.1.1 Background

Non-small cell lung cancer is the most common cause of cancer death worldwide. In the EU the crude incidence of lung Cancer is 52.5 patients per 100,000 individuals each year with a mortality rate of 48.7 per 100,000/year. Mortality and incidence rates are very similar, due to low survival of these patients. In the developed world lung cancer remains the commonest reason of cancer death in both men and women, although mortality rates for men are dropping. Among men the incidence and mortality rates are 82.5 and 77.0 per 100,000/year, respectively, and for women these rates are 23.9 and 22.3 per 100,000/year, respectively. Non-small cell lung cancer (NSCLC) comprises 80% of reported lung cancer cases and the majority of its new cases are diagnosed in an advanced stage, once it represents a disease for which there is no established screening. Survival statistics are among the worst for any malignancies, and have not improved in the last years. Indeed, nowadays the median survival for lung cancer is 6–12 months from the time of diagnosis with an overall 5-year survival of 5–10%. Nowadays surgery (lobectomy/pneumonectomy plus mediastinal lymph node dissection) offers the best chance of cure in lung cancer, especially for NSCLC cases. However, only a small part of patients are suitable for curative resection and the majority must rely on non-surgical and adjuvant therapies. For most patients resection was technically unsuitable because of obvious dissemination of disease. Therefore, chemotherapy with palliate purpose to prolong patients' life for few months has been increasingly proved by clinical studies. A common first-line therapy for advanced cases of NSCLC in patients with good performance status (PS) is based on combinations of platinum. Despite the first-line chemotherapy is appropriate, most patients experience disease progression. With regard to second-line systemic treatment (docetaxel, pemetrexed, erlotinib) this may improve the symptoms related to disease and survival of patients. Second-line therapy is administered for disease progression, recurrence, or intolerable adverse effects following administration of initial chemotherapy. In first line, doublet chemotherapy has been found to be superior to single-agent chemotherapy. Platinum-based chemotherapy combined with vinorelbine, gemcitabine or a taxane prolongs survival, improves quality of life and controls symptoms in patients with good performance status. Non-platinum combination

chemotherapy can be considered in patients who are not fit to receive platinum agents. In Second line, in a phase III study, Shepherd and colleagues proved the efficacy of erlotinib against placebo in increasing the survival and reduced symptoms. Erlotinib response rates are higher in non-smokers, women, adenocarcinomas, Asians and patients with EGFR mutations. Several studies show that erlotinib prolongs survival in patients with advanced NSCLC after the failure of first line or second line chemotherapy. In a phase II clinical trial, 57 patients with refractory NSCLC received erlotinib monotherapy and showed a response rate of 12.3% and a median survival of 8.4 months. Based on these results and for a different pharmacological profile, erlotinib was approved by the FDA for the treatment of second and third line NSCLC. Some studies have also shown that mutations in the EGFR gene are associated with response to EGFR TKI.

### 1.1.2 Erlotinib (OSI-774; Tarceva®)

Erlotinib is an orally active and potent inhibitor of tyrosine kinase, which acts on the epidermal growth factor receptor (EGFR) developed for the treatment of solid tumours including NSCLC. The recommended daily dose of erlotinib is 150 mg.

Erlotinib acts via direct and reversible inhibition of the human EGFR tyrosine kinase, with an IC50 of 2 nM (0.786 ng/mL) in an in vitro enzyme assay, and reduces receptor autophosphorylation in intact tumour cells with an IC50 of 20 nM (7.86 ng/mL).

At nanomolar concentrations, erlotinib blocks Epidermal Growth Factor (EGF)-dependent cellular proliferation and inhibits cell cycle progression in the G1 phase. Selectivity testing against a panel of isolated tyrosine kinase demonstrated that erlotinib is selective for the EGFR^13.

The most frequently-reported adverse events (AEs) associated with single-agent erlotinib are rash (dermatosis), diarrhoea, nausea, fatigue, stomatitis, vomiting, and headache. On the other hand, skin rash was identified as a key indicator of erlotinib trough plasma concentrations. These results support those from previous studies on EGFR inhibitors, which have revealed a similar association between drug steady-state plasma concentrations and the intensity of rash and diarrhoea. Laboratory abnormalities, primarily involving changes in liver function tests (elevation of alanine aminotransferase (ALT), aspartate aminotransferase (AST), and/or bilirubin) are less frequently observed with single-agent erlotinib. These abnormalities occur occasionally in patients treated with erlotinib in combination with either gemcitabine, or carboplatin and paclitaxel. Caution should be used when administering Tarceva to patients with hepatic impairment. Dose reduction or interruption of Tarceva should be considered if severe adverse reactions occur.

An indication of completed and ongoing clinical studies on erlotinib in NSCLC can be found in the Investigator's Brochure.

## 2 STUDY OBJECTIVES

### 2.1 PRIMARY OBJECTIVES

The primary objective of this study is to evaluate the anti-tumoral activity of erlotinib (Tarceva®; 150 mg) through objective response rate (ORR) in patients with non-small-cell lung cancer (NSCLC) in locally advanced or metastatic stages who have not received previous chemotherapy for their disease and who present activating mutations in the tyrosine kinase (TK) domain of the epidermal growth factor receptor (EGFR).

[figure not shown]
### 2.2 SECONDARY OBJECTIVES

The secondary objectives of this study are:

- To evaluate progression-free survival (PFS);
- To evaluate the EGFR mutation frequency;
- To evaluate the overall survival (OS);
- To evaluate the erlotinib safety profile (Tarceva®; 150 mg);
- To evaluate response duration.

## 3 STUDY DESIGN

This is a local open-label, multi-centre Phase II study of the anti-tumoral activity of erlotinib (Tarceva®; 150 mg) evaluated by objective response rate (ORR) in patients with NSCLC in locally advanced or metastatic stages who have not received previous chemotherapy for their disease and who present activating mutations in the TK domain of the EGFR. Summary of the study design is shown in Figure 1.

**Figure 1** - Summary of study design

### 3.1 PROTOCOL SYNOPSIS

The protocol synopsis is in Appendix 1. For additional details, see the Study Flowchart in Appendix 2.

## 3.2 STUDY POPULATION

The target populations of this study are patients with histologically or cytologically confirmed locally advanced or metastatic NSCLC who have not received previous chemotherapy for their disease and who present activating mutations in the TK domain of the EGFR.

### Inclusion criteria:

A subject may be included if the answer to all of the following statements is "yes".

1. Patients able and willing to give written informed consent. Consent must be obtained prior to any study-specific procedure.
2.
  - a) Histologically or cytologically documented inoperable, locally advanced or metastatic NSCLC disease;
  - b) Patient that presents activating mutations (exon 19 deletion and/or exon 21 substitution L858R ) in the tyrosine kinase domain of EGFR ;
3. Measurable disease, according to RECIST - Response Evaluation Criteria in Solid Tumours).
4. Male or female patients aged  $\geq 18$  years.
5. Life expectancy  $\geq 12$  weeks.
6. Adequate haematological and coagulation function as assessed by the investigator.
7. Adequate liver and renal function as assessed by the investigator.
8. Female patients must be postmenopausal (24 months of amenorrhea), surgically sterile or they must agree to use a physical method of contraception. Male patients must be surgically sterile or agree to use a barrier method of contraception. Male and female patients must use effective contraception during the study and for a period of 90 days following the last administration of erlotinib. Acceptable methods of contraception include an established hormonal therapy or intrauterine device for females, and the use of a barrier contraceptive (i.e. diaphragm or condoms) with spermicidal.
9. If applicable, patients with asymptomatic and stable cerebral metastases receiving medical treatment will be eligible for the study. Those patients may have received radiation therapy for their cerebral metastases before the initiation of systemic treatment for non-small-cell lung cancer.
10. Able to comply with the required protocol and follow-up procedures.

### Exclusion criteria

A subject will be excluded if the answer to any of the following statements is "yes".

1. Previous treatment with chemotherapy or therapy against EGFR, either with antibody or small molecule (tyrosine kinase inhibitor) for metastatic disease. The administration of neo-adjuvant or adjuvant therapy is allowed as long as it has finalized  $\geq 6$  months before entering the study. Patients can have received radiotherapy as long as the irradiated lesion is not the only target lesion for evaluating response and as long as radiotherapy has been completed before initiating the study treatment (28 days period is recommended). Treatment with an investigational drug agent during the four weeks before enrolment in the study.
2. History of another neoplasm other than carcinoma in situ of the uterine cervix, basal cell skin carcinoma treated adequately, or prostate carcinoma with a good prognosis (Gleason  $\leq 6$ ) treated radically. History of another neoplasm treated curatively and without evidence of disease in the last 5 years. History of breast cancer and melanoma at any time.
3. Patients with symptomatic cerebral metastases.
4. Known hypersensitivity to erlotinib or any of its excipients.
5. Any significant ophthalmologic abnormality, especially severe dry eye syndrome, keratoconjunctivitis sicca, Sjögren's syndrome, severe exposure keratitis or any other disorder likely to increase the risk of corneal epithelial lesions. (The use of contact lenses is not recommended during the study. The decision to continue to wear contact lenses should be discussed with the patient's treating oncologist and the ophthalmologist.)
6. Use of coumarins (Sintrom®; Varfine®). If the patient requires anti-coagulant therapy, instead of coumarins, the use of a low molecular weight heparin is recommended, whenever clinically possible.
7. Patients with severe hepatic and renal impairment as assessed by the investigator.
8. Evidence of any other disease, neurological or metabolic dysfunction, physical examination or laboratory finding giving reasonable suspicion of a disease or condition that contraindicates the use of an investigational drug or puts the patient at high risk for treatment-related complications.
9.
  - a) Positive urine pregnancy test in women of childbearing potential. Female patients should not be pregnant or breast-feeding.
  - b) Patients (male or female) with reproductive potential not willing to use effective method of contraception during the trial and during 90 days after the last erlotinib administration. Oral or injectable contraceptive agents cannot be the sole method of contraception.
10. Patients with pre-existing disease of the lung parenchyma such as lung fibrosis, lymphangitic carcinomatosis.

11. Patients with known infection with HIV, HBV, HCV. Testing is not required in the absence of clinical signs and symptoms suggestive of these conditions.
12. Patients those in the Investigator's opinion are not able to accomplish protocol requirements.
13. Incapacity to take oral medication or previous surgical procedures that affect absorption and imply the need for intravenous or parenteral feeding.

### **3.3 ENDPOINTS**

#### **3.3.1 Primary efficacy endpoint**

The primary efficacy endpoint is ORR defined as the proportion of patients in whom a complete response (CR) or partial response (PR), as per RECIST 1.1, is observed, assessed based on diagnostic imaging.

#### **3.3.2 Secondary efficacy endpoints**

- Progression-free survival, defined as the time from baseline visit to the date of first occurrence of disease progression or death due to any cause.
- Overall survival defined as the time from the baseline visit (first dose of erlotinib) to the date of death due to any cause.
- Frequency of EGFR mutation.
- Response duration, defined as the time of initial response (CR/PR whichever is first recorded) until documented disease progression.

#### **3.3.3 Safety outcome endpoints**

Safety of the treatment will be evaluated by all adverse events using the National Cancer Institute Common Terminology Criteria for AEs (NCI CTC-AE) version 4.0. The incidence of serious adverse events (SAEs) and non-SAEs related to erlotinib therapy will be determined. Additional information about AEs of special interest (serious and non-serious) such as Stevens-Johnson syndrome and interstitial lung disease (ILD) will be collected. Information about laboratory exams (haematology, biochemistry and coagulation), ECG and physical examination will be also collected.

### **3.4 ANALYSIS TIMING**

One interim analysis is planned for the study with a cut-off date on 30th September 2013. This interim analysis will include an epidemiological, efficacy and safety characterization of erlotinib in 1st line EGFR Mut+ mNSCLC Portuguese population.

## 4 STUDY CONDUCT

### 4.1 RANDOMIZATION ISSUES

Not applicable, since this is a single-arm trial (all patients are assigned to treatment). For each patient enrolled in the study, a sequential number will be attributed (01- 30).

### 4.2 DATA MONITORING

See the study Trial Monitoring Plan.

## 5 STATISTICAL METHODS

### 5.1 DETERMINATION OF SAMPLE SIZE

The sample size was calculated based on the primary variable of the study, objective response rate. Since this proportion is unknown an exploratory sample size of 30 patients was considered to evaluate primary endpoint. This sample size will allow estimating ORR with a margin of error of approximately  $\pm 17.5\%$ , for a 95% confidence interval.

Furthermore, approximately 2000 new cases of stage IIIB and IV NSCLC are diagnosed per year in Portugal and, based on published data, expected prevalence of EGFR mutation is approximately 10%. With a 95% confidence interval, it was calculated that at least 420 patients will have to be screened to achieve 30 positive cases for the exploratory sample size analysis.

### 5.2 ANALYSIS POPULATIONS

#### 5.2.1 Intention to treat (ITT) population

Intention to treat population will be defined as all subjects who are enrolled to the treatment phase of the study, regardless if they completed treatment.

#### 5.2.2 Per protocol (PP) population

Per protocol population will include all subjects enrolled in the treatment phase of the study without major protocol violations.

The protocol violations and corresponding impact are listed below.

Category	Impact
Assessment not performed	Minor/Major
Deviations from the dosing of the IPs	Major
Inconsistency with inclusion/exclusion criteria	Major
Non-compliance with the dose reduction schedule	Major
Prohibited concomitant medication	Major
Treatment not discontinued after withdrawal criteria is met	Major
Visit dates not per protocol	Minor

### **5.2.3 Safety population**

All patients who received at least one dose of study medication will be included in the safety population.

## **5.3 ANALYSIS OF STUDY CONDUCT**

A descriptive analysis of all study variables will be done. For continuous variables, the mean, standard deviation (SD), median, maximum and minimum will be computed whereas for categorical variables the absolute (n) and relative frequencies (%) will be described.

All analyses will be performed using SAS version 9.4 (SAS Institute Inc, Cary, USA).

All derived variables to be used in the analysis are described in Appendix 3.

### **5.3.1 Patient disposition**

The number of patients included in this study, as well as the number of screening failures will be described in this section. The reason for study treatment termination will be described (progression of disease, unacceptable toxicity and withdrawal of informed consent or death) together with reason for treatment discontinuation (lost to follow-up, investigator's decision or other reason) through absolute (n) and relative frequencies (%). The number (n) and relative frequency (%) of each study population will be also summarized.

### **5.3.2 Demographics**

The age, smoking duration and average number of cigarettes/day if smoker/ex-smoker at the screening visit will be described using median, mean, standard deviation, maximum and minimum.

Gender and smoking habits (non-smoker, smoker or ex-smoker) will be described using absolute (n) and relative (%) frequencies.

Demographic characteristics will be presented considering the ITT population.

### **5.3.3 Childbearing potential/Pregnancy test**

For female patients, the childbearing potential and contraception method at the screening visit will be described using absolute (n) and relative (%) frequencies. If a female patient is of childbearing potential, the incidence of pregnancy tests performed and respective result (positive/negative) will be evaluated.

The number of men who uses a contraception protection, or who are surgically sterilized or naturally sterile or abstinent or have a partner surgically sterile will also be assessed using frequencies.

The childbearing potential/pregnancy test information will be collected at the screening visit, baseline visit and at the end of study treatment.

Results will be presented considering the ITT population.

### **5.3.4 Medical history**

#### **5.3.4.1 NSCLC Diagnosis**

The disease duration (in years) at the screening visit will be described using median, mean, standard deviation, maximum and minimum. The diagnosis technique (histology/cytology), pathology results (adenocarcinoma, bronchoalveolar carcinoma, large cell carcinoma, squamous cells carcinoma, mixed cell type or other), TNM classification (T, N and M)) and location of metastatic disease (adrenal glands, liver, brain, bone or other) will also be described using absolute (n) and relative (%) frequencies.

#### **5.3.4.2 Co-morbidities**

The number of patients having any co-morbidity at the screening visit will be assessed. For patients with co-morbidities, the frequency of patients in grade 1 to 5, or with mild, moderate, severe, life threatening or disabling severity or death related will be described.

Results on medical history will be presented considering the ITT population.

### **5.3.5 ECOG performance status**

The absolute (n) and relative (%) frequencies of patients with performance status information at each visit will be assessed as well as its respective result using median, mean, standard deviation, minimum and maximum.

Results will be presented considering the ITT population.

### **5.3.6 Concomitant medications**

The absolute (n) and relative (%) frequencies of patients taking any concomitant medication will be assessed.

Concomitant medication will be presented considering the ITT population.

### 5.3.7 Tumour assessment

The absolute (n) and relative (%) frequencies of patients with a pre-existing CXR, a chest and upper abdomen CT Scan or MRI, an isotope bone scan, a brain CT Scan or a brain MRI will be described for each visit. For patients with any of these exams performed, the proportion of patients with abnormal clinically relevant exam results will be evaluated. Tumor assessment using the RECIST criteria (Appendix 5) will be carried at baseline, within +/- 5 days of the 8-weekly assessments and at the end of study treatment visit. For tumor assessments completed outside the scheduled time, results will be analyzed as part of the nearest scheduled visit.

Results on tumour assessment will be presented considering the ITT population.

### 5.3.8 Clinical response (RECIST criteria)

At each planned time point, the overall response (complete response (CR), partial response (PR), stable disease (SD), or progressive disease (PD)) will be assessed for each patient, taking into account both target and non-target lesions, as per RECIST criteria. This will be summarized as the percentage of patients reaching each level of response at that time point. At the end of the study treatment, best overall response will be determined for all patients and presented as percentages of patients with each level of response.

In addition, for each study visit the number of patients with lesions evaluated through CT Scans, MRIs or Spiral CT Scans will be described, as well as the percentage of patients with target and non-target lesions placed at the brain, liver, lymph nodes, bones, skin, peritoneum, lung or other location.

Results on clinical response will be presented considering the ITT population.

### 5.3.9 Efficacy analysis

In this trial, the efficacy endpoints will be analyzed for ITT and PP population. The ITT analysis will be considered as the primary analysis.

#### 5.3.9.1 Primary Efficacy Endpoint

The primary efficacy endpoint is the objective response rate (ORR) defined by the number of patients with complete response (CR) or partial response (PR) as the best overall response during the treatment period divided by the total number of patients based on diagnostic imaging according to RECIST 1.1 (see Appendix 5). The ninety five percent (95%) confidence interval will be estimated for the ORR.

### **5.3.9.2 Secondary Efficacy Endpoints**

The secondary efficacy variables include:

- Progression-free survival (PFS), defined as the time from baseline visit to the date of first occurrence of disease progression or death for any cause while the patient was under study or during the prolonged follow-up period. PFS will be summarized as median time and will be estimated using the Kaplan-Meier method. Ninety five percent (95%) confidence interval will be estimated for median time to PFS.
  
- Overall survival (OS), defined as the time from the first dose of erlotinib to the date of death due to any cause while the patient was under study or during the prolonged follow-up period. Overall survival variable will be summarized as median time to OS and will be estimated using the Kaplan-Meier method. 95% confidence interval will be estimated for median time to OS. The date of first dose is not captured in the study CRF. Therefore, for this endpoint it will be assumed that the patient will take the first dose at the day of the baseline visit.
  
- Epidermal growth factor receptor (EGFR) mutation frequency. The presence of EGFR mutation (exon 19 deletion and/or exon 21 substitution L858R) in the study population will be presented as the relative frequency of those mutations among the total screened patients. A 95% confidence interval will be estimated for this value using binomial distribution.
  
- Response duration, defined as the time of initial response (CR/PR whichever is first recorded) until documented tumor progression. Response duration will be summarized as median time and will be estimated using the Kaplan-Meier method. Ninety five percent (95%) confidence interval will be estimated for median time to response duration.

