A recent phase III study (OPTIMAL) of first line treatment with erlotinib compared to platinum-based chemotherapy (gemcitabine/carboplatine), in Asian population with NSCLC with EGFR mutation has shown a median PFS of 13.1 months in the erlotinib arm with HR=0.16 (95% CI; 0.10-0.26) versus 4.6 months in the chemotherapy arm. It has also shown an ORR of 82.9% in the erlotinib arm versus 36% in the chemotherapy arm (p<0.0001)²⁵. Erlotinib should therefore be considered in preference to first line chemotherapy in patients with this distinct disease.

Considering the potential benefit for patients in initiating erlotinib earlier in their treatment it becomes crucial to evaluate its anti-tumoral activity through a more sensitive and accurate endpoint such as objective response rate during first-line treatment in Caucasian populations.

In this trial erlotinib will be given in first-line treatment for advanced NSCLC with EGFR mutation positive.

Although this trial is a non-randomized phase II trial, Erlotinib is currently used in clinical practice to treat NSCLC²⁶. Any patient with locally advanced or metastatic non-small cell lung cancer disease found to have an EGFR exon 19 deletion or exon 21 mutations will be offered first-line treatment with erlotinib having ORR as primary efficacy endpoint.

EGFR mutations rates in Portugal

Previous studies with gefitinib have shown the incidence of mutations to be around 8% in unselected patients, whereas studies conducted in Asia show mutation rates of 19-60% In the Spanish Lung Cancer Group study of erlotinib that included only Spanish patients with EGFR mutations the EGFR mutation rate was 16.6%. In this trial, the population was mainly female, non-smokers and adenocarcinoma. The EGFR mutation's rate amongst

NSCLC patients, in Portugal is currently unknown so that the health burden and economic implications of treatments directed specifically at patients with this characteristic cannot be accurately assessed.

Therefore one of the objectives of the current study is to assess the EGFR mutation rate in Portugal NSCLC population. This will be done by testing Portuguese patients newly diagnosed with recurrent or metastatic NSCLC for the EGFR mutations.

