2.2 Secondary Objectives

To evaluate progression-free survival (PFS), defined as the time from baseline visit to the date of first occurrence of disease progression or death due to any cause.

To evaluate the EGFR mutation frequency, in the study population.

To evaluate the Overall Survival defined as the time from baseline visit to the date of death due to any cause.

To evaluate the erlotinib safety profile (Tarceva[®]; 150 mg).

To evaluate response duration (RD) defined as the time of initial response (CR/PR whichever is first recorded) until documented disease progression.

[figure not shown]

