5.2 Procedures for Enrolment of Eligible Patients

Once a patient has fulfilled the entry criteria, will be enrolled in the study, beginning with the EGFR mutation testing at the Central Laboratory [REDACTED] by Sequential Technique. A surgical fragment or biopsy formalin-fixed, paraffin-embedded or a tumour material obtained through aspiration cytology fixed and paraffin-embedded in a cell-block, must be sent to the Central Laboratory [REDACTED]. If activating mutations (exons 19 and 21 mutations) in the TK domain of EGFR gene are identified, patients are eligible to participate in the study. Although, for methodological issues, mutations will be identified from the exon 18 to 21, but only patients with Exon 19 deletion or exon 21 substitution L858R in the TK domain of EGFR gene will be enrolled in this trial.

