8.2.1.2. Secondary Variables

PFS will be summarized as median time and will be estimated through Kaplan-Meier method. 95% confidence interval will be estimated for median time to PFS.

Overall survival variable will be summarized as median time to OS and will be estimated through Kaplan-Meier method. 95% confidence interval will be estimated for median time to OS.

The presence of EGFR mutation in the study population will be presented as relative frequency presented as a percentage (%). A 95% confidence interval will be estimated for this value using binomial distribution.

Response duration variable will be summarized as median time to response duration and will be estimated through Kaplan-Meier method. 95% confidence interval will be estimated for median time to response duration.

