**Table 16 – Epidermal growth factor receptor – All patients**

	Total (n=xx)
EGFR test performed, n(%)	
Yes	
No	
Total	
EGFR positive result, n (%), 95% CI	
Positive	
Negative	
Total	
Exon 19 and/or exon 21 mutations, n (%)	
Exon 19	
Exon 21	

Positive result: patients with Exon 19 and/or exon 21 mutations.

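### The SAP gives two different numerators for the EGFR mutation frequency, and neither is the unrestricted mutation rate that the protocol names as its objective

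*SAP*

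**What the plan says.** The protocol states the aim without naming mutation types. Section 1.3 says that "one of the objectives of the current study is to assess the EGFR mutation rate in Portugal NSCLC population", section 2.2 has "To evaluate the EGFR mutation frequency, in the study population", and the analysis text in 8.2.1.2 has "The presence of EGFR mutation in the study population will be presented as relative frequency presented as a percentage".

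Protocol 5.2 separates what the laboratory detects from what makes a patient eligible: "mutations will be identified from the exon 18 to 21, but only patients with Exon 19 deletion or exon 21 substitution L858R" go on to enrolment.

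SAP 5.3.9.2 brings the eligibility definition into the frequency endpoint. It counts "The presence of EGFR mutation (exon 19 deletion and/or exon 21 substitution L858R) in the study population" and reports "the relative frequency of those mutations among the total screened patients", with a binomial 95% CI.

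SAP Table 16 has only a Positive and a Negative row for the test result, followed by rows for exon 19 and exon 21. Its footnote reads "Positive result: patients with Exon 19 and/or exon 21 mutations". No table shell has a row for exon 18 or exon 20.

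**The concern.** Two things are at stake.

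The first is internal. The numerator of a named secondary endpoint depends on whether the programmer follows the text of 5.3.9.2 or the footnote of Table 16. The CI is requested in both places, so two intervals could result from the same data.

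The second is interpretation. Protocol 1.3 calls the Portuguese mutation rate unknown and sets out to assess it. A figure reported simply as the EGFR mutation rate, but built from two mutation types, would be read as something wider than it is. In addition, a category labelled Negative could contain patients in whom the laboratory found an EGFR mutation.

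**Working it through.** **Step 1: classify each possible laboratory result under the two SAP definitions.**

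| Sequencing result | SAP 5.3.9.2 text | SAP Table 16 footnote |
|---|---|---|
| Exon 19 deletion | counted | Positive |
| L858R (exon 21) | counted | Positive |
| Other exon 19 mutation | not counted | Positive |
| Other exon 21 mutation | not counted | Positive |
| Exon 18 mutation only | not counted | Negative |
| Exon 20 mutation only | not counted | Negative |
| No mutation in exons 18–21 | not counted | Negative |

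Rows 3 and 4 are the contradiction. Rows 5 and 6 are detected mutations that share a label with row 7. This step needs no assumption about how common any mutation is.

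**Step 2: reproduce the plan's screening figure.** Inputs from SAP 5.1: prevalence "expected prevalence of EGFR mutation is approximately 10" per cent, 30 positive cases wanted, 95% confidence, at least 420 patients. Require the lower normal limit for the number of positives to reach 30:

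n × 0.10 − 1.96 × √(n × 0.10 × 0.90) ≥ 30

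The solution is n = 420.6, that is 421, which agrees with the stated 420. I use N = 420 below, taking all 420 as tested. At 10% this gives 42 patients. The Clopper-Pearson 95% CI for 42/420 is 7.3% to 13.3%.

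**Step 3: size the gap between the eligible rate and the any-mutation rate.** Let q be the share of patients with an EGFR mutation in exons 18–21 who have neither exon 19 deletion nor L858R. The documents give no value, so q is an assumption. Then

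eligible rate = (1 − q) × any-mutation rate.

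If the eligible rate is 10.0% (42/420):

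| Assumed q | Patients with any mutation, 42/(1 − q) | Any-mutation rate | Not counted by 5.3.9.2 |
|---|---|---|---|
| 0% | 42.0 | 10.0% | 0 |
| 5% | 44.2 | 10.5% | 2.2 |
| 10% | 46.7 | 11.1% | 4.7 |
| 20% | 52.5 | 12.5% | 10.5 |
| 30% | 60.0 | 14.3% | 18.0 |

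The any-mutation rate passes the upper limit of the interval (13.28%) at q = 1 − 10/13.28 = about 25%. Below that it lies inside the CI of the eligible rate.

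The last column is also the most that could sit under Negative in Table 16, because the other exon 19 and exon 21 mutations are Positive there. For the same reason it bounds the difference between the SAP's two numerators. At q = 10% they differ by between 0 and 4.7 patients, at most 4.7/420 = 1.1 percentage points.

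**Step 4: the other reading of the planning 10%.** SAP 5.1 does not say which mutations the 10% covers. If it means any EGFR mutation, the eligible rate is 0.10 × (1 − q), or 9.5%, 9.0% and 8.0% for q of 5%, 10% and 20%. The step 2 formula then asks for 444, 469 and 528 screened patients instead of 421.

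**The case against.** The best defence is that 5.3.9.2 names the mutations it counts. That is a disclosed definition, and the figure estimates it validly. There is also a reason for it. Protocol 1.3 wants the rate in order to judge the burden and cost of treatments aimed at patients with this characteristic, and for sizing that group the eligible rate is the useful one. Protocol 5.2 attributes the wider exon reading to methodological reasons, not to an endpoint. The Table 16 footnote may be shorthand: the protocol synopsis and 5.2 both speak loosely of exon 19 and 21 mutations while meaning the two specific types.

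Much of this stands. The eligible rate should be kept, and the footnote may be no more than loose wording. But the programmer still has two definitions to choose from, and the shorthand does not explain why exon 18 and 20 findings should be called Negative. The unrestricted wording in protocol 1.3, 2.2 and 8.2.1.2 also remains unanswered.

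Three stronger readings are tempting, and the documents do not support them:

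- A reader might infer that every patient with another EGFR mutation is labelled Negative. Under the Table 16 footnote, any exon 19 or exon 21 mutation is Positive; only mutations confined to exon 18 or 20 fall under Negative.
- A reader might infer that the rate is simply understated. That holds only if the figure is taken as the any-mutation rate and q is above zero.
- A reader might infer that the interim analysis sets this rate against published rates. The comparison in protocol 3.3 concerns preliminary clinical benefits; the mutation rate is listed separately, with no comparison mentioned. Protocol 1.3 does quote published rates (about 8%, 16.6%, 19–60%) but does not say which mutations they cover, so the direction of any mismatch with them is unknown.

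**Conclusion.** The contradiction between SAP 5.3.9.2 and the Table 16 footnote is established from the text alone, as is the placing of exon 18-only and exon 20-only mutations under Negative. The effect on the reported rate is conditional. Against an any-mutation reading, an eligible rate of 10.0% is 0.5 to 2.5 percentage points low for assumed q of 5% to 20%. This stays within sampling error at 420 patients and is nil if q is 0. It is systematic, however, so testing more patients would not remove it.

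Severity is minor. The endpoint is descriptive with no hypothesis test (protocol 8.2.2), and ORR, PFS, OS and the 30 treated patients are not touched. The 420 screening figure is affected only if the planning 10% meant any EGFR mutation.

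**What to change.** In SAP 5.3.9.2 and Table 16:

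1. Use one definition of the eligible result, exon 19 deletion and/or L858R, and correct the Table 16 footnote to match.
2. Report two rates, each with an exact 95% CI: the eligible rate as just defined, and the rate of any mutation in exons 18–21. The second answers the objective as the protocol words it.
3. Add rows for exon 18, exon 20, other exon 19 and other exon 21 mutations.
4. Reserve Negative for patients with no mutation detected in exons 18–21.

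The cost is SAP wording and a few table rows. The sequencing is already planned. The one practical burden is that mutation types may have to be transcribed from laboratory reports if the eCRF does not hold them. The sponsor's own estimate is kept.
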